18.0 Confidentiality

All information obtained from the participants will remain strictly confidential and will not be released except at the express written request of the study participant. All electronic data will be maintained on an AHC-IS secure server folder and a Box folder backup. Per University of Minnesota and the School of Public Health security guidelines, participant data will be maintained on the AHC-IS secure project folder for approximately 3-5 years which is the time anticipated it will take to disseminate any and all research papers or presentations from these data. Similarly, paper forms of the data will be located in a locked file cabinet in [name] ([name] research office) only accessible to the research team. Unless the data are being filed or accessed, these cabinets will remain locked.

The PI, research coordinator, and graduate research assistants will plan on creating a tracking file for the purposes of interview reminders and completion of the various data collection procedures. However, it is important to note that in the data analysis files, no identifying information will be entered or included. Any hard copy forms collected by LSS-MN staff (e.g., SCs) will be maintained in a locked file cabinet at LSS-MN and will be transferred securely to [name] and [name] at the conclusion of the project. SCs will be asked not to collect or record any personal health information on their clients.

Similar to our other IRB-approved protocols, we will utilize a secure (or encrypted) telephone-based recording system to conduct semi-structured interviews. The XBlue X-7 or Olympus DS-2600 recording systems have the ability

PROTOCOL TITLE: Utilizing Senior Companions to Enhance Dementia Care Services and Supports: R61 Phase

VERSION DATE: 10/28/22; IRB Approved 11/1/22

to record both sides of a telephone conversation. The device connects to a computer for upload to a secure environment. The recordings are saved to the UMN Box Desktop App and the AHC-IS project server folder. Recorded telephone interviews will be transcribed using Production Transcripts services.

19.0 Provisions to Monitor the Data to Ensure the Safety of Participants

As the proposed project will pose minimal risks to study participants, the Principal Investigator (PI), [name], will serve as the primary monitoring entity of this study. As noted in the Protection of Human Research Subjects section, the proposed study involves no invasive procedures and there will be no physical risks to study participants. The consideration of need is potentially stressful, and thus there are possible psychological risks for the PWML or caregiver. However, potential participants with a history of serious mental illness (i.e., any major psychiatric disorder) will not be included in the study.

Specifically, if a participant indicates they have clinical depression or a similar mental illness whose: a) symptoms have exacerbated in the last six months, and b) are not receiving steady, ongoing pharmacological or other treatment for these symptoms during the screening procedure, they will be excluded from our project. Further, since the research team has considerable experience providing psychosocial support to dementia caregivers on various research protocols, serious psychological risks are unlikely to occur. The potential social or legal risks for the participants relate only to possible violations of confidentiality. With respect to private information entered, the design of the system will include a structure of permissions with password protection to limit access to materials so only dementia caregivers and the research staff can view sensitive information.

Additional monitoring support will be provided by the Independent Study Monitor (ISM), [name], Mayo Professor and Head of the Division of Health Policy and Management in the University of Minnesota School of Public Health.

A. Data and Safety Monitoring Procedures: Monitoring Study Safety

B1. Monitoring study safety. In addition to ongoing review of the protocol and human subjects research compliance during weekly project meetings with staff, the PI ([name]) will generate annual reports to ensure that each case complies with Institutional Review Board (IRB) requirements, including use of IRB-approved forms (particularly the consent form), and that each staff person on the proposed project adheres to the study protocol. In both weekly meetings and audit reports, [name] will actively work with project staff to minimize research-associated risk and protect confidentiality of participant data (see Protection of Human Research Subjects section). The research coordinator and research assistants will be trained to interview in ways that are non-threatening, friendly, and respectful. We will emphasize to all participants that they do not have to complete any question they do not want to answer, and that the

PROTOCOL TITLE: Utilizing Senior Companions to Enhance Dementia Care Services and Supports: R61 Phase

VERSION DATE: 10/28/22; IRB Approved 11/1/22

interview may be terminated at any time according to their wishes. We will stress to PWML, their caregivers, and SCs who deliver the intervention that their decision to discontinue the study will in no way affect the services they are receiving from the University of Minnesota, Lutheran Social Service of Minnesota (LSS-MN), or other entities.

In the event that a caregiver does become upset during the survey or interview process, the research coordinator or research assistant will contact [name], who will be available for consultation. If a caregiver is in crisis because of their care situation or for some other reason, research staff will be instructed to consult with [name]. With the caregiver's permission, we will then contact the appropriate resource person in an external agency (e.g., the Alzheimer's Association). Based on the research team's experience working with their caregiving families, we expect very few or no such instances to occur. If a member of the research team does identify neglect or other potentially inappropriate care practices, the state Ombudsman will be notified to protect the rights of persons with dementia and their families.

All information obtained from the participants will remain strictly confidential and will not be released except at the express written request of the study participant. All electronic data will be maintained on [name] office computer and the School of Public Health shared project folder. Per University of Minnesota and the Academic Health Center-Information Systems data security guidelines, all data on [name] AHC shared server are protected by strong passwords only accessible to [name] or the research team. The data will be maintained on [name] AHC server folder for approximately 3-5 years which is the time anticipated it will take to disseminate any and all research papers or presentations from these data. Similarly, paper forms of the data will be located in a locked file cabinet in [name] ([name] research office) only accessible to the research team. Unless the data are being filed or accessed, these cabinets will remain locked.

B2. Annual audit reports. The responsibility of [name] (who also have oversight for the data management and analysis of the project) will include the production of an annual report that will highlight the results of the audit analysis, as well as study progress. In addition, [name] will provide information on any deviations from the approved protocol (e.g., deviations in adhering to study eligibility criteria), error rates, and any other issues related to the progress of the study. The ISM will review the audit report to ensure ongoing quality control, and will work with [name], if needed, to ascertain if audited cases deviate from the approved study protocol. In instances of adverse events occurring (see below) the University of Minnesota IRB will be notified.

PROTOCOL TITLE: Utilizing Senior Companions to Enhance Dementia Care Services and Supports: R61 Phase

VERSION DATE: 10/28/22; IRB Approved 11/1/22

The audit reports will include the following:

1. Table of contents
2. Narrative/trial summary
 - a. Summary of main findings
 - b. Discussion of issues or problems
 - c. Report preparation procedures
3. Study description
 - a. Project organizational chart, personnel
 - b. Brief statement of purpose of trial
 - c. Projected timetable and schedule
4. Study administration
 - a. Recruitment and participant status
 - i. Table 1: Enrollment by year or month of study
 - ii. Figure 1: Comparison of target to actual enrollment by month
 - b. Forms status
 - i. Status of forms (e.g., consent, completing of screener, baseline assessment battery, etc.)

B3. Reporting Adverse Events and Unanticipated Problems

In addition to ongoing monitoring of protocol and human subjects compliance and reporting and the production of annual case audits, [name] will generate safety reports on an ongoing basis that will list adverse events, serious events, unanticipated events, events related to or associated with the intervention, and the potential causality of the intervention to the event for each participant should they occur. Taken from the National Institutes of Mental Health policy on Data and Safety Monitoring in Clinical Trials and the Guidance on Reporting Adverse Events to Institutional Review Board for NIH-Supported Multicenter Trials (as suggested in the Policy of the National Institute of Nursing Research for Data and Safety Monitoring of Clinical Trials), the definition of each event is as follows:

Adverse event. Any untoward medical occurrence in a patient or clinical investigation participant that does not necessarily have to have a causal relationship with the treatment. An adverse event can therefore be any unfavorable and unintended sign (including an abnormal laboratory finding, for example), symptom, or disease temporally associated with the use of [an intervention], whether or not considered related to the [interventions].

Serious adverse event. Any adverse experience that results in any of the following outcomes: death, a life threatening experience, inpatient hospitalization, a persistent or significant disability/incapacity, or a congenital anomaly/birth defect. Important medical events that may not result in death, be life threatening, or require hospitalization, may be

PROTOCOL TITLE: Utilizing Senior Companions to Enhance Dementia Care Services and Supports: R61 Phase

VERSION DATE: 10/28/22; IRB Approved 11/1/22

considered a serious adverse drug experience when based upon appropriate medical judgment, they may require medical or surgical intervention to prevent one of the outcomes listed in this definition.

Unanticipated Problem. Any adverse experience, the specificity or severity of which is not consistent with the risks information described in the [protocol or consent documents].

Related to (or associated with) the intervention. There is a reasonable possibility that the experience may have been caused by the intervention.

Causality. A reasonable possibility that the product is etiologically related to the adverse event. Causality assessment includes, for example, assessment of temporal relationships, dechallenge/rechallenge information, association with (or lack of association with) underlying disease, presence (or absence) of a more likely cause, plausibility, etc.

In the instance of an adverse event, [name] will classify whether the event is unanticipated, adverse, or seriously adverse, whether the event is unanticipated or related to the intervention, and what potentially caused the event. [name] will review study-related data on an ongoing basis, will alert the University of Minnesota IRB as they occur, and will document adverse events in their annual report for the ISM and NIA program officer if these events occur. Specifically, [name] will utilize an adverse event form that will provide detail on the occurrence (who, what, when, where, why if relevant) of any adverse, serious adverse, unanticipated event/problem, and whether these events were related to participation in the proposed project. If adverse events occur during the R61 Phase of the project, the PI will review and report adverse events to the Institutional Review Board at the University of Minnesota. In our annual Data Safety and Monitoring Report, we will provide these adverse reports to the Independent Study Monitor to review and approve via a signed cover letter. The final, approved Data Safety and Monitoring Report would then be sent to the Program Officer at NIA for review.

B4. Procedures to Ensure Compliance with the Monitoring Plan across Study Sites
Not applicable.

B5. Assessment of External Factors

[name], via his own research experience as well as his editorial board service, is kept abreast of developments in ADRD caregiver interventions. This proximity to cutting-edge research on family caregiving interventions in addition to his regular review of the literature he conducts to support his various dissemination efforts will allow the research team to assess issues related to the delivery of community-based services and supports to PWMLs and their family caregivers. If such developments reveal any potential threats to participant

PROTOCOL TITLE: Utilizing Senior Companions to Enhance Dementia Care Services and Supports: R61 Phase

VERSION DATE: 10/28/22; IRB Approved 11/1/22

safety or other concerns that require protocol modification, these issues will be addressed in the annual audit reports provided to the ISM and the University of Minnesota IRB.

B6. Plans for Interim Analysis

There are no planned interim/futility analyses. Interim analyses are not planned because in the R61 Phase of this project, there is no randomly assigned control condition; the objective of the R61 Phase is to initially implement and refine the PorchLight Project's content, structure, and delivery where needed in preparation for the subsequent R33 Phase (years 3-5). For these reasons, we did not deem futility analyses appropriate.

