14.0 Risks to Participants

Since the study involves no invasive procedures, there will be no physical risks to study participants. The consideration of need is potentially stressful, and thus there are possible psychological risks for the caregiver. However, the research team has considerable experience providing psychosocial support to dementia caregivers on various protocols and serious psychological risks are unlikely to occur based on this experience. The potential social or legal risks for the participants relate only to possible violations of confidentiality. Given the procedures outlined below, such risks are highly unlikely.

In creating our research design and sampling procedures, an important objective was to preserve the privacy, confidentiality, and autonomy of all participants.

As indicated above, the experience of the research team and the exclusion of PWML and caregivers with serious psychiatric illness will minimize the possibility of psychological risks. The unlikelihood of such problems is evident from the absence of any clinically significant problems during the past 13 years that the research team has operated various protocols related to dementia caregiving intervention research. The research coordinator and research assistants will be trained to interview in ways that are non-threatening, friendly, and respectful. We will emphasize to all participants that they do not have to complete any question they do not want to answer, and that the interview may be terminated at any time according to their wishes. We will stress to caregivers, PWMLs, and SC-Ds that their decision to discontinue the study will in no way affect the services they are receiving from the University of Minnesota, Lutheran Social Service of Minnesota (LSS-MN) or other entities.

In the event a caregiver or PWML does become upset during the interview process, the research coordinator or research assistant will contact [name], who will be available for consultation. If a caregiver or PWML is in crisis because of their care situation or some other reason, research staff will be instructed to consult with [name]. With the caregiver's permission, we will then contact the appropriate resource person in an external agency (e.g., the Alzheimer's Association). Based on the research team's experience working with their caregiving families, we expect very few or no such instances to occur. If a member of the research team does identify neglect or other potentially

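### Section 19.0 B3 gives an ordinary confidentiality breach, a harm the protocol itself names, no assured route to the adverse event form, the ongoing safety report or the prompt IRB alert

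*Combined protocol and SAP*

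**What the plan says.** **Harms named.** Sections 14.0 and 19.0 say there is no physical risk. They allow for psychological risk, because thinking about need can be stressful. On the social and legal side, section 14.0 says: "The potential social or legal risks for the participants relate only to possible violations of confidentiality". Section 19.0 repeats this.

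**Event definitions (section 19.0, B3).** An adverse event is "Any untoward medical occurrence in a patient or clinical investigation participant", whether or not it is related to the intervention, and the scope sentence adds: "An adverse event can therefore be any unfavorable and unintended sign (including an abnormal laboratory finding, for example), symptom, or disease". The serious adverse event text includes congenital anomaly as an outcome and speaks of an event being "considered a serious adverse drug experience when based upon appropriate medical judgment". The causality text refers to a product and to dechallenge and rechallenge. An unanticipated problem is "Any adverse experience, the specificity or severity of which is not consistent with the risks information described in the" protocol or consent documents.

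**What the definitions control.** B3 provides for ongoing safety reports listing the defined events, an adverse event form, an alert to the IRB as events occur, and an annual report to the Independent Study Monitor (ISM) and the NIA program officer. B2 adds: "In instances of adverse events occurring (see below) the University of Minnesota IRB will be notified".

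**Handling of distress and neglect.** Sections 10.0, 14.0, 19.0 (B1) and 25.0 describe what staff do. In B1, for example: "If a caregiver is in crisis because of their care situation or for some other reason, research staff will be instructed to consult with" a designated team member, after which an outside resource is contacted with permission. Neglect findings go to an outside body.

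**The concern.** A minimal-risk psychosocial study should at least be able to count the harms it says it could cause. B3 casts a wide net for medical events in older people with memory loss, related or not. It does not say how a breach is to be classified, and it does not connect the distress and neglect procedures to any study record.

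Opportunities for a breach exist. Companions write a log and journal entry after each contact (section 5.0). The community partner holds hard-copy forms, and recorded interviews go to an outside transcription service (section 18.0).

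If a breach occurred and staff followed B3 as written, the safety report could show nothing. A reader could then take the blank entry as support for section 14.0's view that confidentiality risks are very unlikely, when it might only reflect the classification rule.

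**Working it through.** No arithmetic applies. The plan gives no figure on this point, and the documents give no incidence for any of these incidents. The check sets each kind of incident against each B3 definition, then looks for another written route in sections 10.0, 14.0, 18.0, 19.0, 20.0 and 25.0.

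| Incident | Adverse event? | Unanticipated problem? | Other written route |
|---|---|---|---|
| Ordinary confidentiality breach | No: not a sign, symptom or disease | Not clearly: the risk is described; only if it departs from the description in specificity or severity | Annual B2 audit report, as a deviation or issue |
| Distress or crisis | Possible: as a symptom, related or not | Not clearly: the risk is described | Consultation, then an outside resource with permission |
| Neglect or inappropriate care | No, unless it produces a medical event | Possible: not listed as a study risk in 14.0 or 19.0 | Outside body |

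1. **Breach.** It fails the adverse event definition because it is not medical. The serious category requires outcomes such as death, hospitalization or disability, so it does not help. The unanticipated category turns on inconsistency with the described risks, and a breach is the one social or legal risk described. The safety report also lists events related to the intervention, but B3 defines that term as a judgment about cause. Even read as a class of its own, it would not reach a breach in research data handling.

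2. **Consequence.** The adverse event form, the ongoing safety report and the as-they-occur IRB alert all attach to these classes, so an ordinary breach has no assured route to any of them.

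3. **Other route.** The B2 audit report covers protocol deviations and has a heading for issues and problems. The ISM reviews it, and B5 describes the annual audit reports as going to the ISM and the IRB. B1 ties weekly meetings and audit reports to protecting confidentiality. This route exists, but it is annual and general, and it requires no count of breaches.

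4. **Distress and neglect.** Each has a possible reading that brings it into B3. None of the four sections describing the steps mentions the adverse event form, so whether an incident is recorded depends on who classifies it.

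5. **A contradiction found on the way.** Section 10.0 directs neglect findings to the county Adult Protection office. Sections 14.0, 19.0 (B1) and 25.0 direct them to the state Ombudsman.

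**The case against.** The strongest case against is that the plan already has the routes it needs. Confidentiality is a protocol commitment, so a breach is a deviation, and B2 reports deviations to the ISM without using the B3 definitions. The unanticipated-problem test covers specificity as well as severity. The protocol describes the risk only in general terms, so a concrete breach might qualify, and the term adverse experience is not limited to medical events. Distress is a symptom and counts whatever its cause. Neglect is not a described risk, so nothing excludes it as unanticipated. The stated sources of the definitions are NIH-level monitoring policy and reporting guidance.

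Most of this stands, and it rules out several stronger readings. A reader might infer that a breach reaches no safety report at all; the B2 audit report and the specificity limb show otherwise. A reader might infer that distress is excluded; the symptom wording allows it in. A reader might infer that the definitions were taken from medical product trials; the protocol says otherwise, and only the wording has that character. A reader might also put an expected number on the missed incidents; any rate would be invented, and the protocol expects very few or none.

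What the objection does not supply is a sentence in B3 that classifies an ordinary, anticipated breach, or any link from the distress and neglect steps to the form. The B2 route does not replace the ongoing safety report or the prompt IRB alert.

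**Conclusion.** The point holds as a gap in classification and recording. Of the two harms the protocol names, confidentiality breach meets no B3 class clearly, and psychological distress meets one only if someone chooses to call it a symptom. Neglect findings are left to judgment in the same way. A breach would appear at most in the annual audit report as a deviation or issue, unless it was judged worse than, or different in kind from, the described risk.

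No number can be put on the effect. The conclusion rests on reading B3's adverse event definition as medical, which is its plain wording, and on the protocol's own risk description counting as the benchmark for unanticipated problems. The consent pages were not available, so what they say about breach could not be checked. The documents do not say that the R33 phase will rely on a zero count. The narrower conclusion is that a blank entry for these harms would not be evidence of their absence.

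**What to change.** In B3, state that each known or suspected confidentiality breach is a reportable study event, entered on the existing adverse event form whether or not the protocol or consent form lists the risk. On the same form, log each use of the crisis or distress procedure and each neglect notification. Show these in the safety report and final report as a separate count of families, apart from intercurrent medical events. This changes recording only, not how any incident is managed.

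The revision table records the study as completed. The practical step now is to tabulate these incidents from existing records where those allow, say so where they do not, and correct B3 before the R33 phase reuses it.

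Separately, section 10.0 must be reconciled with sections 14.0, 19.0 (B1) and 25.0 on which body receives a neglect notification.

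The cost is a wording change, one more table line, a few more forms for existing staff, and a harm count that may not be zero.
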